## **E4. Adequacy of Protection Against Risks**

### **Procedures to Minimize Drug-Related Risks**

We will screen very carefully for alcohol use and depressive symptoms. It will be made explicit that participants are not to drink alcohol in evening. We will use the Alcohol Use Disorders Identification Test (AUDIT) score and our mental health counselors SCID-screener to enroll only those with low risk for alcohol abuse. Subjects will report no current depressive symptomatology (Beck Depression Inventory, or BDI < 15), with no past depressive episodes or suicidal ideation. The Columbia Suicide Severity Rating Scale (CSSRS) will be administered at each visit (see additional details below), as per NIH/FDA  UTHealth Houston s. Indication of regular IRB NUMBER: HSC-MS-19-0966 IRB APPROVAL DATE: 10/12/2023

alcohol use by AUDIT score, intake self-report, or breath alcohol, or indication of increase in depressive symptomatology / suicidality as measured by the CSSRS will result in study stopping (see details below). Will exclude for any patients taking CYP3A inhibitors; patients with severe hepatic impairment; and women who are or become pregnant. Pregnancy and drug tests are administered on via urinalysis on lab testing days. Women of childbearing capacity must be taking one form of birth control. We will exclude for women with BMI > 30 to decrease risk of side effects.

In addition to the rigorous screening criteria for inclusion. At the end of each experimental day, cardiovascular measures will be taken and the subject will be evaluated for signs of impairment or side effects, first by a research assistant and then by the research nurse, medical director, or PI. The assessment battery includes subjective effects questionnaire, nystagmus, touching nose, balance, and walking a straight line). If cardiovascular measures are normal, within the range of pre-dose levels, and the subject is determined to be unimpaired, the subject will be released. If any signs of intoxication are detected, participants will be required to remain at the experimental site until such symptoms are no longer observed.

In the event of either an unexpected adverse event or a prolonged period of intoxication, we have several measures in place. First, [name] (CNRA medical director) has clinical experience and training in emergency medicine. Thus, a physician will be in the immediate vicinity of laboratory at all times. Offices and clinical space are within 100 feet of the lab. Collaborating MDs can be paged at any time during the day. Second, Ben Taub Hospital, a level 5 emergency medical center is located just minutes away from BBSB. Finally, in the event of extended sedation, intoxication, or impairment, in which any subject does not appear clear-headed, feeling well, and in full control of his or her behavior, two steps will be taken. First, the subject will remain in the lab until such time that the primary or a co-investigator deems that it is safe for him or her to leave (e.g., passing the sobriety test described above). In the event of extended impairment, we will arrange (and pay for) a taxi service to drive the subject back to his/her home rather than having to use METRO. We will administer the Columbia Suicide Severity Rating Scale (CSSRS screening version) at each visit to assess suicidality and depressive symptoms, consistent with current FDA best practices. If the screening indicates change in suicidal ideation, we will administer the full version. If suicidality is judged to clinically significant as per CSSRS scoring criteria, we will (1) report the event to CPHS within 48 hours; (2) remove the patient from the study; (3) make a referral to either the BBSB outpatient mood disorders clinic or UT HCPC, depending on consultation from Dept of Psychiatry outpatient faculty at BBSB.

For the cold pressor task, participants will be told that if the level of pain is too uncomfortable, they should remove the hand immediately and not wait to the end of the 120 sec test period. Each participant will be able to test the water temperature for 10 sec prior to beginning the procedure. These details are presented in the informed consent document. Because there are no sustained effects of cold water, if a participant cannot sustain the immersion for 120 sec at baseline, it will not preclude repeated testing on the follow-up lab test day.

**Other Protections Against Risk.** The following procedures will be taken to safeguard against adverse medication events: (1) careful initial intake evaluation to determine eligibility based on inclusion/exclusion criteria; (2) thorough physical evaluation prior to treatment, consisting of physical examination, standard laboratory tests, electrocardiogram, toxicology screen, pregnancy test, and vital signs; (3) repeated tests during treatment; (4) daily monitoring of pill taking using MEMS caps, returned pill counts, and self-report; (5) weekly review of adverse events and medication compliance; (6) regular evaluation by the study physician ([name]). Specific criteria will be used to exclude potential subjects for whom any of the study medications is contraindicated. Any abnormal physiological, psychological, or behavioral event will be evaluated and, if indicated, will result in the subject's removal from the study.

For all three experiments included in this project, we will use an Adverse Event Log (AEL) based on NIDA SAFTEE procedures. The AEL will record the duration, severity, and frequency of any adverse events, signs, and symptoms. An evaluation will be made as to the event's relationship to the study drug(s), scaled as unrelated, unlikely, possible, and probable. The AEL will be included in 1   IRB APPROVAL DATE: 10/12/2023

Subjects will be monitored regularly for compliance with the study requirements, including the dosing regimen and breath alcohol testing upon arrival at the laboratory each day of testing. Written and verbal information about the medication will be given to all participants. This information will remind the subject to: (1) take food shortly after medication if needed to relieve gastric irritation; (2) inform the treatment research clinic nurse or physician of any over-the-counter and prescription medication taken, especially: cough medication, diarrhea medication, narcotic medication; (2) notify treatment research clinic nurse or physician of any side effects that persist or worsen. The study physician, nurse, and PI will review cases involving clinical deterioration of increased symptomatology or substance abuse. Appropriate actions will be taken, including study termination with proper referral.

Confidentiality will be protected in several ways. All information collected solely for research purposes will be kept in locked, restricted access files. Individual subject information will be transferred to outside sources only with the express written request of the subject. Subjects will receive a copy of their signed consent form. All personnel associated with this grant have successfully completed ethics training in the Protection and Welfare of Human Participants, and certification is on file at the Health Science Center CPHS and office of sponsored projects. All intake and experimental data that are collected will be uploaded onto a laboratory database, computers dedicated to data storage and management. These computers are protected by password. All data will be treated as confidential information. All data including urine samples, medical and psychiatric intake exams, and behavioral and drug administration data – will be obtained solely for research purposes. All individuals who elect to participate and sign the informed consent agreement will be assigned a subject number (e.g., 3200), which will serve as that subject's identifier (rather than name or SS#). A log book and electronic database that connect participants' identifying information with subject number are kept in a locked file cabinet and room and password protected, respectively.

**Recruitment and Informed Consent.** Participants will be self-referred in response to various study advertisements. All CNRA recruitment materials have been approved by CPHS for ongoing studies over the past 5 years. Individuals who call for information will be given a brief description of the study. Those interested will then be asked to answer questions about their current substance use. A trained research assistant will conduct this telephone-screening interview. Eligible subjects will be scheduled for an in-person intake visit at the CNRA, first floor BBSB. The first intake appointment will begin with the presentation of the informed consent form. The consent form will detail the requirements of study participation (e.g., # of visits, type of data collected, time commitment, etc.).

Subjects will be told that the purpose of the study is to evaluate the effects of medications on human behavior related to mood, sleep, and cigarette smoking. Information about the components of the experimental procedure will be explained. Details of the random assignment procedure (placebo or active dose) will be explained. Subjects will be informed of their attendance expectations. Other information on the consent form will include a full description of study requirements, reimbursement, risks, benefits, alternatives, and the role of the local IRB. All questions will be answered before written consent is requested. All research conducted in our laboratory and the CNRA has prior approval from the Committee for the Protection of Human Subjects (CPHS) of the University of Texas Health Science Center - Houston.

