### **Measures**

**Baseline Screening** As part of the CNRA general evaluation protocol (HSC-MS-05-0322), to determine eligibility, participants will receive a comprehensive medical and psychiatric evaluation including: a medical-history questionnaire, physical examination, laboratory chemistries (e.g., blood chemistry screen, complete blood count, urinalysis and urine pregnancy test), and ECG. Clinicians will conduct the **SCID**, the **ASI**, the **KMSK** assessment of lifetime substance use interview, and **TLFB**.

**Smoking-Related Measures** Nicotine dependence will be assessed using the **FTND**. Self-report will be used to collect self-reported number of cigarettes used in the past 7 days. Nicotine craving will be assessed using a brief, 10-item version of the **Questionnaire of Smoking Urges (QSU-brief)**. Nicotine withdrawal will be assessed using the 8-item **MNWQ**. **Breath CO** will be used to measure severity of smoking and overnight smoking abstinence.

**Sleep-Related Measures** Quality of sleep in the past week will be primarily assessed using the **PROMIS Sleep Disturbance Short Form**, a well validated and reliable subjective measure of sleep quality. Secondary measures will include the **Epworth Sleepiness Scale**, and **PSQI**. Sleep actigraphy (total hours, levels, and movement) will be measured via the Garmin Vivosmart® 3 device as validated by recent research.

**Stress and Anxiety Measures** Stress and anxiety will be assessed using standard, validated questionnaires using the **HAM-A**, **PSS**, and **DASS-21**. Additionally, a single-item **VAS** measure will be used to assess self-reported stress.

**Human Laboratory Measures** Experimental measures will be conducted on study days 1 and 8. Participants will be instructed to stop smoking by 10 pm the day before, in order to ensure they meet the breath CO criterion ( $CO \leq 4$  ppm) indicating overnight abstinence. In addition to measuring nicotine craving and withdrawal using the QSU and MNWQ, respectively, we will conduct two additional assessments.

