## DATA SAFETY MONITORING PLAN

### **E1. Human Subjects Involvement and Participant Characteristics**

The study will test 20 current cigarette smokers, 18 to 65 years old that report smoking at least 10 cigarettes/day (half pack). Notably, because the study medication (suvorexant) is contraindicated with alcohol use, we will exclude subjects with alcohol use disorders (via screening at intake). We will also exclude those individuals meet DSM-5 criteria for an alcohol use disorder or report recent problem drinking (5/4 drinks for males/females in < 2.5 hours or > 10 alcoholic drinks per week) or those who report being unwilling to stop using alcohol in the evening for the two weeks of the study. Additional exclusion criteria include individuals that are pregnant, nursing, or planning on becoming pregnant during the course of the study; or if they have any other illness, condition, or use of medications which in the opinion of the PI and/or admitting physician would preclude safe and/or successful completion of the study. This will be accomplished via full medical evaluation at intake by [name], M.D., CNRA Medical Director. The study will be conducted at the Neurobehavioral Research Laboratory at the CNRA. Recruitment strategies will include local advertising in print media, public service announcements on radio, and referrals to CNRA in the Houston metropolitan area. We expect to enroll a minimum of 2 participants per month to meet recruitment goals; however, we will be able to accommodate four simultaneous participants. Participants will be required to participate for 3 days (intake/screening, baseline observations, and one follow-up observation one week later). Research data will be collected at each scheduled time point.

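### No alcohol question is scheduled in the dosing week, and breath tests on Days 1 and 8 cannot reach most of the seven dosing nights

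*Combined protocol and SAP*

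**What the plan says.** **Restriction.** E4 (Procedures to Minimize Drug-Related Risks) states: "It will be made explicit that participants are not to drink alcohol in evening". The exclusion criterion in Participant Recruitment and Setting, repeated in E1, is also limited to evenings and runs for the two weeks of the study.

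**Stopping rule.** The same part of E4 ends participation on an indication of regular "alcohol use by AUDIT score, intake self-report, or breath alcohol, or indication of increase in depressive symptomatology" (a page break in our copy falls just before these words). AUDIT and self-report are described only as screening or intake measures.

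**Timing.** E4 (Other Protections Against Risk) provides for "breath alcohol testing upon arrival at the laboratory each day of testing". Human Laboratory Measures says "Experimental measures will be conducted on study days 1 and 8". E1 lists three attendance days: intake, "baseline observations, and one follow-up observation one week later". Study Medication & Medication Compliance sets the dose at 10 PM, and Table 1 gives seven days of drug from Day 1.

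**Other safeguards.** E4 lists a daily check on pill taking, "weekly review of adverse events and medication compliance", and physician evaluation. It adds that "The study physician, nurse, and PI will review cases involving clinical deterioration of increased symptomatology or substance abuse". Participants are reminded to "inform the treatment research clinic nurse or physician of any over-the-counter and prescription medication taken" and to report side effects; the listed reminders do not mention alcohol. E2 says urine as well as breath is collected for alcohol detection. Table 1 places the Timeline Followback (TLFB) at baseline only.

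**Risk.** Participant Recruitment and Setting, E1 and E10 call suvorexant contraindicated with alcohol. E3 names narcolepsy as the contraindication and treats alcohol as raising the listed risks. The point is the same on either reading.

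**The concern.** The protocol treats alcohol with this drug as a safety matter and has a rule to stop participants over it. After enrolment that rule has one named input, and the input is read once before the first dose and once after the last. If a participant drinks on Day 3, nothing scheduled would show it in time to act, and probably nothing would show it afterwards.

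Two things are at stake. The first is safety. People who drink up to 10 drinks a week can enter, and on the protocol's wording a daytime drink breaks no stated restriction although drug from the night before is still present. The second is interpretation. Staff must grade each adverse event by its relationship to study drug, and alcohol raises the same sedation-type risks. Daytime sleepiness is also measured as an outcome (Epworth). With 10 participants per arm and no alcohol record for Days 1 to 7, one or two drinkers could colour either arm's sleepiness or adverse event profile, and nobody could tell.

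**Working it through.** The plan states no figure on this point, so there is none to reproduce. The check is the timeline, followed by what each alcohol measure can see.

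1. **Doses against tests.** Doses fall at 10 PM on Days 1 to 7, spanning 6 × 24 = 144 h from first to last. Breath tests are on arrival on Days 1 and 8. That the Day 1 test precedes dose 1 is inferred from the 10 PM dose time. Doses between the two tests: 7 of 7. The Day 1 test can still prevent all dosing; the next reading follows dose 7.

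2. **Alcohol questions between the visits.** TLFB, ASI and KMSK are at baseline only. The past-week self-report under Smoking-Related Measures covers cigarettes. The daily check covers pills. The weekly review covers adverse events and medication compliance. Scheduled alcohol questions: 0.

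3. **Look-back of the Day 8 breath test.** Hours to undetectable = peak ÷ elimination rate. Neither input is in the documents. Assuming peaks of 0.03 to 0.12 g/dL and elimination of 0.010 to 0.020 g/dL per hour:
   - shortest: 0.03 ÷ 0.020 = 1.5 h
   - longest: 0.12 ÷ 0.010 = 12 h

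   Assume arrival 10 to 16 h after dose 7. Dose 6 is then at least 10 + 24 = 34 h back, well outside 12 h. The test can reach the evening of dose 7 at best, and only after heavier or later drinking. Nights 1 to 6 are out of reach.

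4. **Drug on board at the Day 8 test.** At the stated half-life of about 12 h, the fraction of the dose-7 level left is 2^(−10/12) = 0.56 at 10 h and 2^(−16/12) = 0.40 at 16 h. The Day 8 test is therefore taken with drug present.

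5. **Drug on board by day.** From a 10 PM dose, 2^(−14/12) = 0.445 remains at noon and 2^(−20/12) = 0.315 at 6 PM. With 24 h dosing, accumulation is 1 ÷ (1 − 2^(−2)) = 1.333, giving 0.594 and 0.420 of the first dose's bedtime level at steady state. This assumes one compartment and instant absorption. These are concentrations, not risks.

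6. **Urine.** E2 gives no assay, visit or look-back for alcohol. E4 puts urine drug and pregnancy tests on laboratory testing days, and urine is not among the named alcohol triggers. Its reach cannot be computed.

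7. **Effect of adding contacts.** Asked before the 10 PM dose, a Day 4 question splits the seven doses into runs of 3 and 4; Days 4 and 6 split them into 3, 2 and 2. The longest unchecked run falls from 7 to 4 or to 3.

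**The case against.** The strongest reply is that the drug is given at an approved dose for seven nights, to people screened as low risk on AUDIT. E10 also excludes frequent regular alcohol use. There is an evening bar and a breath test at both laboratory visits. E4 says compliance with study requirements is monitored regularly, in wording that is not exhaustive. It also provides for regular physician evaluation, and E10 adds a side-effects profile at each visit and a medical examination at study end. Staff can remove a participant at any time.

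Much of this stands, and it limits the priority. It does not fill the gap: none of these items is described as asking about alcohol between Day 1 and Day 8, and those tied to visits share the same two dates. Screening lowers the expected amount of drinking but is not a record of it. The protocol also screens for pregnancy and suicidality, yet checks both again at visits.

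Three stronger readings are tempting and not supported:

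- A reader might infer that nothing scheduled can detect drinking while drug is present. The Day 8 breath test is taken with drug on board and could catch drinking around dose 7, and the unspecified urine test may see further.
- A reader might infer that participants are told in writing that daytime alcohol is acceptable. E4 does not say that the evening instruction is written. The consent form and medication sheet are not in our copy and may say more.
- A reader might multiply the entry ceiling, 10 drinks a week, by the 10 participants on active drug and take 100 drinks as the exposure. That ignores the low-risk and frequent-use screens and is not an estimate of anything.

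**Conclusion.** The concern holds in a limited form. No alcohol self-report is scheduled in the dosing week. Breath alcohol, the only named alcohol trigger after enrolment, is read outside all 7 doses and cannot reach at least 6 of the 7 dosing nights. The alcohol stopping rule, followed as written, therefore cannot act between the first and last dose. The stated restriction is evening-only, with roughly 45% of the bedtime level left at noon and 31% at 6 PM.

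The timeline rests on the documents alone, apart from the inferred order on Day 1. The look-back rests on assumed alcohol kinetics and arrival times, and the remaining drug fractions on a simple half-life model. None of it shows that anyone would be harmed, and the general power to remove a participant is unaffected. This is a cheap improvement of optional to moderate priority, not a flaw that undermines the trial.

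**What to change.** 1. **Ask during dosing.** Add one alcohol question to the existing pill-taking self-report or to the compliance texts mentioned in E9, for example on Days 4 and 6 before the 10 PM dose. Any reported drinking goes to the study physician, who decides case by case whether dosing continues. An automatic hold is not advised. On the model above, the level after dose 7 would be 0.988 of full steady state if dose 4 were held (1.333 − 4^(−3) = 1.318; ÷ 1.333), but 0.812 if dose 6 were held (1.333 − 4^(−1) = 1.083; ÷ 1.333), just before the only post-treatment assessment. Log any held dose and analyse the participant as randomised.

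2. **Record it at Day 8.** Repeat the TLFB for alcohol, covering Days 1 to 7, and list it by arm beside the adverse event log. The TLFB is already used at baseline, and the reference cited for it is an alcohol manual.

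3. **Widen the restriction.** Keep the two-week evening bar. Subject to the medical director's agreement, add no alcohol at any time from Day 1 until at least 24 h after the last dose, that is, to 10 PM on Day 8. By then 2^(−24/12) = 25% of the level after dose 7 remains.

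**Cost.** One amendment; 2 × 20 = 40 contacts; a few minutes at Day 8; no extra visit. If 10% to 30% of contacts report drinking (an assumption), there are 40 × 0.10 = 4 to 40 × 0.30 = 12 physician calls. There may be a few more screen failures.

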**Table 1. Outline of procedures and assessments**

	BL	Day 1	Day 8
Baseline Screening Physical Exam, Medical History, Labs, ECG, Urine Pregnancy Test, SCID, ASI, KMSK, TLFB	X		
Smoking Related Measures FTND QSU, MNWQ, Self-Report, Breath CO	X X	X	X
Stress/Anxiety Related Measures HAM-A, PSS, DASS-21, VAS	X	X	X
Sleep Related Measures PROMIS Sleep Disturbance Short Form, Epworth, PSQI Actigraphy Sleep Monitoring (Garmin Vivosmart® 3)	X	X	X
Receive 7 days of suvorexant (0 or 20 mg)		X	
Relapse Risk Assessment Stress Reactivity Assessment (HR, BP, salivary cortisol, VAS) Dual-Component Smoking Relapse Assessment		X X	X X

**SCID** - Structured Clinical Interview for DSM-5, **ASI** - Addiction Severity Index; **KMSK** - Kreek-McHugh-Schluger-Kellogg scale; **TLFB** - Timeline Followback; **FTND** – Fagerstrom Test for Nicotine Dependence; **QSU** – Questionnaire on Smoking Urges-brief; **MNWQ** – Minnesota Nicotine Withdrawal Questionnaire; **CO** – Carbon Monoxide; **HAM-A** – Hamilton Anxiety Rating Scale; **PSS** – Perceived Stress Scale; **DASS-21** – Depression Anxiety Stress Scales; **VAS** – Visual Analog Scale; **PSQI** – Pittsburgh Sleep Quality Index; **HR** – Heart Rate; **BP** – Blood Pressure

**Participant Recruitment and Setting (N = 20, n = 10/group)** will consist of otherwise healthy, cigarette smokers that report smoking at least 10 cigarettes/day, are between 18 and 65 years old and fluent in English, without greater than mild substance use disorder on drugs other than nicotine. Because suvorexant is a sedative-hypnotic contraindicated with alcohol use, participants will be excluded if they: meet DSM-5 criteria for an alcohol use disorder; report recent problem drinking (5/4 drinks for males/females in < 2.5 hours or > 10 alcoholic drinks per week); report being unwilling to stop using alcohol in the evening for the two weeks of the study; are pregnant, nursing, or planning on becoming pregnant during the course of the study; or if they have any other illness, condition, or use of medications which in the opinion of the PI and/or admitting physician would preclude safe and/or successful completion of the study. Recruitment strategies will include local advertising in print media, public service announcements on radio, and referrals to Center for Neurobehavioral Research on Addiction (CNRA) in the Houston metropolitan area. We will also recruit from the Department of Psychiatry Recruitment Registry: HSC-MS-23-0768.

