**Research Team PI: [name].** [name] is an Assistant Professor in the Department of Psychiatry & Behavioral Sciences, with a primary research program involving novel applications of biostatistics and data science to health outcomes. However, his recent endeavors have expanded to first-hand research in substance use disorders and psychopharmacology, resulting in two pertinent first-author publications investigating (1) the effects of suvorexant on relapse-related factors in cocaine use disorder and (2) the strongest predictors of the first smoking lapse during a quit attempt. The present study will be supported by the infrastructure and research team at the CNRA, including **[name].**, a frequent collaborator of the PI that will assist in the implementation of the current experimental design, and mentorship from **[name].**, with expertise in psychopharmacology and the neurological bases for addiction.

**Study Medication & Medication Compliance** Participants will be randomized to receive either suvorexant 0 or 20 mg for 7 days. 20 mg is currently the highest FDA-approved dose. The bioavailability of suvorexant is > 80% and it is highly protein-bound, with a half-life of approximately 12 hours and plasma steady-state is reached within three days. Because suvorexant is a hypnotic with a moderate half-life, participants will be informed to take the medication at 10:00 PM. Compliance will be assessed using both Medication Event Monitoring Systems (MEMS) pill bottles that record the time/frequency of bottle openings as well as riboflavin.

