## **E3. Potential Risks**

**Suvorexant** (BELSOMRA) is an orexin receptor antagonist indicated for the treatment of insomnia, characterized by difficulties with sleep onset and sleep maintenance. Recommended dose is 10 mg, 1x per night taken within 30 minutes of going to bed, with at least 7 hours of planned time before awakening. If the 10 mg dose is well tolerated but not optimally effective, it can be increased but not to exceed 20 mg once daily. Medication is taken PO, with dosage in tablets of 5, 10, 15, and 20 mg. Contraindicated in patients with narcolepsy. Precautions include daytime somnolence; dose-related risk of impaired alertness and motor coordination, including impaired driving; patients taking 20 mg should be cautioned against next-day driving; nighttime “sleep-driving” and other complex behaviors while out of bed and/or not fully awake; worsening of depression or suicidal thinking; compromised respiratory function; sleep paralysis, hypnagogic/hypnopompic hallucinations. Risk of the above symptoms increases with use of CNS depressants and alcohol. In obese women (BMI > 30), there is increased risk of exposure-related adverse effects. Belsomra is a schedule-IV compound with mild/modest abuse-potential in the same class as existing sleep medications and anxiolytics. The most common adverse reactions include somnolence and slowed motor coordination. Not recommended for use in patients taking strong CYP3A inhibitors, efficacy may be reduced, or for patients with severe hepatic impairment. Based on animal data, Belsomra may cause fetal harm.

**Risks for Behavioral and Psychometric Testing.** Items on certain psychological/psychiatric questionnaires and interviews might be perceived as personally discomforting to some subjects. Similarly, subjects may experience discomfort due to withdrawal symptoms as part of the smoking relapse assessment. With regard to the actigraphy sleep monitoring, participants may experience mild discomfort while acclimating to wearing the device during sleep. While subjects may be uncomfortable reporting these issues, the risks of serious sequelae are extremely low.

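### For suicidality that emerges after the first dose, the first scheduled CSSRS is on Day 8, after 7 of 7 doses (6 of 7 if dosing starts on Day 2)

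*Combined protocol and SAP*

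**What the plan says.** **Assessment.** Section E4, Procedures to Minimize Drug-Related Risks, states "We will administer the Columbia Suicide Severity Rating Scale (CSSRS screening version) at each visit to assess suicidality and depressive symptoms". A change in ideation leads to the full version. Clinically significant suicidality leads to a report to the IRB, removal from the study and referral. The same section gives the stopping rule: "indication of increase in depressive symptomatology / suicidality as measured by the CSSRS will result in study stopping (see details below". Table 1 does not list the CSSRS.

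**Visits.** Section E1: "Participants will be required to participate for 3 days (intake/screening, baseline observations, and one follow-up observation one week later". Table 1 places the last two on Day 1 and Day 8.

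**Dosing.** Table 1 marks "Receive 7 days of suvorexant (0 or 20 mg" in the Day 1 column. Under Study Medication & Medication Compliance, "participants will be informed to take the medication at 10:00 PM".

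**Risk.** Section E3 lists "worsening of depression or suicidal thinking" among the precautions for suvorexant.

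**Other routes to stopping.**
- E4, Other Protections Against Risk, describes repeated tests, daily monitoring of pill-taking, weekly adverse event review, regular physician evaluation, and removal where an abnormal psychological event calls for it. The physician, nurse and principal investigator also review clinical deterioration.
- The same part covers participant information. "This information will remind the subject to", among other things, "notify treatment research clinic nurse or physician of any side effects that persist or worsen".
- E9 adds continued medical monitoring and compliance texts.
- E10, Referral to Treatment, ends participation if depression or suicidal ideation is found to be at risk level. It names no instrument and sets no assessment day.

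**The concern.** The protocol names a psychiatric risk of the drug and lists a CSSRS-triggered stop among its measures against drug-related risk. A stopping rule of that kind protects a participant by ending exposure, so it has to be applied while doses remain. Here the instrument is tied to visits, and the two visits on either side of treatment are a week apart with the whole supply dispensed at the first. If ideation changes on drug, the dated check finds it when little or nothing is left to withhold. During the week, stopping depends on the participant volunteering the problem, or on staff noticing it through a contact that has no stated day or is not described as asking about mood.

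**Working it through.** **Inputs**
- CSSRS at each visit (E4).
- Three visits: intake, Day 1, Day 8 (E1, Table 1).
- Seven doses, one each evening at 10 PM, supplied on Day 1 (Table 1; Study Medication & Medication Compliance).
- Visits in the daytime (E10, Special Considerations Across the Lifespan, refers to daytime participation).
- The evening of the first dose is not stated. Both Day 1 and Day 2 are worked through as assumptions.

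**Step 1: is there a paid interim visit?** The plan's own figure is a maximum compensation of $234 (Study Compensation). With two visits after screening: 40 + 2×50 + 50 + 2×5 + 34 = 234, an exact match. With a third, and the $34 held fixed: 40 + 3×50 + 50 + 3×5 + 34 = 289. The payment schedule has no room for another paid visit.

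**Step 2: doses left at each CSSRS.** Doses left at a daytime check on Day c = number of dosing days on or after c.

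| Check | Doses on Days 1–7 | Doses on Days 2–8 |
|---|---|---|
| Day 1 visit | 7 left | 7 left |
| Day 8 visit | 0 left (7 taken) | 1 left (6 taken) |
| Added Day 4 call | 4 left (3 taken) | 5 left (2 taken) |

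The interval without a scheduled CSSRS is 8 − 1 = 7 days. With a Day 4 call the longest interval is max(4 − 1, 8 − 4) = 4 days.

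**Step 3: limits of a single call.** The Day 4 call helps only if the change has already appeared, that is after doses 1 to 3 (Day 1 start) or doses 1 to 2 (Day 2 start). To illustrate, suppose a change is equally likely to appear after each of the seven doses. The documents do not support or contradict that assumption. The mean number of stoppable doses is then:
- Day 1 start: plan 0/7 = 0.0; with the call (3×4 + 4×0)/7 = 12/7 = 1.7.
- Day 2 start: plan (6×1 + 0)/7 = 0.9; with the call (2×5 + 4×1 + 0)/7 = 14/7 = 2.0.

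On the same basis a Day 3 call gives 10/7 = 1.4 or 11/7 = 1.6, and a Day 5 call gives 12/7 = 1.7 or 15/7 = 2.1. The exact day is not critical. These means count doses on a calendar and do not measure safety benefit.

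**Step 4: does any other provision supply a dated ideation check?** Daily monitoring concerns pill-taking, and the documents do not say that it asks about mood or involves live contact. A weekly review in a seven-day course need not occur before the last dose. The repeated tests, physician evaluation and medical monitoring have no stated day. The full side effects profile is tied to laboratory visits (E10, Safety of Research Participants Outside of the Research Site). The monitoring committee meets annually (E9). None of them schedules a question about ideation between Day 1 and Day 8.

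**The case against.** The case for leaving the plan alone has real weight. Exposure is seven doses at a dose within the approved maximum, with about ten people on active drug. Entry requires a BDI below 15 and no past depressive episodes or ideation (E4), and Axis I disorders other than substance use disorders are excluded (E10). The CSSRS is already used at every visit, which E4 describes as in line with current FDA practice, and nothing in the documents requires a check between visits one week apart. Several other routes to removal exist, including a second ideation-based termination rule in E10. A telephone screen also brings work of its own, because a positive answer off site needs an urgent response.

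Most of this stands, and it limits the priority. It does not close the gap. Entry screening lowers baseline risk but cannot detect a change on drug, and the other routes have no dated ideation check.

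Two stronger readings are tempting and should be resisted. A reader might infer that the CSSRS rule can prevent no doses at all. That is wrong: the Day 1 CSSRS comes before the first 10 PM dose, and a positive result then can prevent all seven. A reader might also infer that participants go unmonitored during the week. The documents do not support that either, given the reporting, monitoring and removal provisions in E4, E9 and E10.

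**Conclusion.** The point holds for suicidality that emerges after the first dose. The first scheduled CSSRS is then Day 8, after 7 of 7 doses if dosing starts on Day 1 and 6 of 7 if it starts on Day 2, so the rule can prevent 0 or 1 dose. The count rests on daytime visits and on the unstated start evening, for which both cases are given. The Day 8 check still serves reporting and referral. Because the documents give no frequency of ideation change on drug, neither expected harm nor events averted can be claimed. This is a cheap improvement of modest priority.

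**What to change.** Add one telephone CSSRS screener for all 20 participants at about Day 4, made by existing staff, with the Day 1 pre-dose screener as the reference.

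- **On any change:** hold the drug and have the on-call physician complete the full CSSRS the same day, with emergency referral if needed.
- **If clinically significant:** apply the report, removal and referral steps already in E4.
- **Otherwise:** record whether dosing resumes. Keep the participant's Day 8 assessments, with missed doses recorded.

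In the text this means adding the CSSRS and a mid-course column to Table 1, and extending the E4 paragraph with the call and the response to a positive screen. Stating the evening of the first dose would remove the remaining ambiguity. The cost is 20 short calls, a written same-day response path for positive screens, and possibly a few missed doses. No clinic visit is added, and the outcomes and sample size do not change.
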